The intervention effect will be tested in the framework of generalized linear mixed effects models^{42,43} with a treatment dummy variable, surgeon random effect and site-by-time dummy variables to control site-specific secular trends.

All models will be estimated and tested using SAS version 9.3 (SAS Institute, Cary, NC), specifically PROC MIXED and PROC NLMIX.

We do not plan to impute missing data if the rate of missingness is low. Currently, our rate of missingness is quite low: 97% of patients and 92% of family members have completed T1. For T2, 88% of patients and 86% of family members have completed the survey and for T3 87% of both patients and family members have completed their survey. We plan to exclude variables for which there is no response (rather than impute these variables). Although we have a small number of incomplete audio recordings, we will treat audio recordings where less than half of the encounter with the surgeon was captured (a total of 6 recordings) as completely missing and those with more than half recorded as complete. We will perform sensitivity analysis to test whether this small loss of data impacts our findings by comparing the outcomes with and without inclusion of audio recordings that are more than half complete.

Aim-1 primary outcomes [Question Counting, PEPPi-5]

Aim 1 has five primary outcomes and as such will be analyzed with a Type I error rate of $\alpha=0.01$.

For question counting, we consider four specific types of questions and evaluate them with ordinal categories:

- Number of OPTIONS questions asked by patients and family members (0, 1, 2+)
- Number of EXPECTATION questions asked by patients and family members (0, 1, 2+)
- Number of ADVANCE DIRECTIVES questions asked by patients and family members (0, 1+)
- Number of RISKS questions asked by patients and family members (0, 1, 2+)

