Power calculations for Aims 1 and 2 were updated to harmonize with the final analysis plan and the realized recruitment, which had a slight reduction in patient-level sample size (from 240/240 control/treatment to 222/221 control/treatment, given that the stepped-wedge study design wave rollover rules were not dependent on intervention assignment). The overall design is retained (relative to the submitted proposal) and the power numbers remain robust. Notably, surgeon-level sample size has not changed, and it is this sample size that is primarily driving the power. We have not modified the assumption that the between-surgeon variance accounts for 30% of the total variance. As noted previously, this is conservative considering preliminary data suggests this variance is as low as 5%.

Under our modified plan, there are four endpoints in Aim 1, the four question types. In this case, tests will be conducted with nominal $\alpha=0.05/4 = 0.0125$. Supported by our preliminary data, we assume a worst-case scenario of 65% of control patients will be in the non-activation set (the zero category). We consider an odds-ratio of improved category (moving to a higher category of questions asked) in the treatment (relative to control) of 1.3. Under these settings, we have 85% power to detect a treatment difference in [Q-Advance Directives]. For each of the other three categories, we have over 93% power to detect a difference. Under our modified protocol, regret is the only endpoint in Aim 2. In this case, testing will be conducted with nominal $\alpha = .05$. We assume the upper bound risk of regret is 0.3; we will have over 91% power to detect a regret risk difference of 0.23.

This additional analysis of our primary endpoints is otherwise unchanged from our per-protocol plan. Our modified analysis will compare the effectiveness of the QPL intervention relative to usual care on patient engagement. We will use an intention to treat (ITT) analysis using all available data from participants based on group assignment. The intervention effect will be tested in the framework of generalized linear mixed effects models with a treatment dummy variable, surgeon random effect and site-by-time dummy variables to control site-specific secular trends. Again, we will consider four specific types of questions and evaluate them with ordinal categories:

- Number of OPTIONS questions asked by patients and family members (0, 1, 2+)

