- Number of EXPECTATION questions asked by patients and family members (0, 1, 2+)
- Number of ADVANCE DIRECTIVES questions asked by patients and family members (0, 1+)

-Number of RISKS questions asked by patients and family members (0, 1, 2+)

Denote each question type with [Q-type], where type is either Options, Expectation, Advance Directives, or Risks. [Q-Advance Directives] is a binary variable, the other three types are three-category ordinal variables. Accordingly, a logistic random effects model will be used to analyze [Q-Advance Directives], while ordinal logistic random effects models will be used for analyzing the other three types.

For Aim 2, there is no change to the modeling approach for regret: we will use a logistic random effects model. We will use an intention to treat analysis using all available data from participants based on group assignment. We will use a logistic random effects model with a treatment dummy variable, surgeon random effect and site-by-time dummy variables to control site-specific secular trends.

Additional considerations: Aim-1 question asking

After performing the ITT analysis, we will restrict the analysis by removing the dyads (patient and family member) where major surgery was not discussed or the patient did not have a vascular or oncologic problem. This is based on the T0 transcript of the conversation with the surgeon, which confirms whether the patient discussed surgery with the surgeon and had a vascular or oncologic problem. Specifically, we will use the subgroup analysis document, coded by the primary coder and confirmed in group consensus, to identify enrolled patients for whom surgical treatment was not discussed, or on evaluation after enrollment, the patient did not make entry criteria to be in the study, specifically, the patient did not have a diagnosis of cancer or vascular disease.

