Next, we will further restrict the analysis based on penetrance of the intervention. We will identify patients in the intervention group with a clear signal that they received the QPL prior to the visit with the surgeon. This will be identified by one or more of the following criteria 1) clear presence or use of the QPL in the audio recorded conversation with the surgeon (noted in less than 20 transcripts), 2) coder identification of something that could be the QPL used during the conversation with the surgeon (coder marked this as unsure), 3) affirmative answer on the T1 survey from the patient or family member that they received something that might be the QPL from the surgeon prior to clinic visit (using a sensitivity analysis based on the certainty around receipt of the QPL within the response to this question), 4) a maybe answer on the T1 survey, 5) notes from the research coordinator that the patient was seen in clinic with a QPL.

Additional analysis will adjust for age and comorbidity. We will also evaluate a composite endpoint of all 4 question types where each of the 4 question types is categorized as binary and the composite score is ordinal (0, 1, 2, 3, 4) such that 4 signifies that a question of each type has been asked.

Additional considerations: Aim-2 regret

We will first consider regret as a binary outcome and then do additional analysis with regret considering this as a categorical variable with 0 = neither patient or family member has regret, 1 = either patient or family member has regret, 2 = both patient and family member have regret.

Stratified Analysis: Aim-2 MYCaW

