Surgeons will be stratified by study site and randomly assigned within each site to cross over from usual care to the QPL intervention in different study waves. On study commencement, a master's level statistician established a step-wise randomisation using a computer-generated randomisation schedule for the list of enrolled surgeons by site. The schedule determined the crossover wave for each surgeon and was designed to balance transitions to the intervention arm across sites in each wave according to the design in table 1. Surgeon crossover will occur in one direction only, and each within-site change will happen once every 4 months during the 24-month duration of the study. A 2-week hiatus in data collection at the start of the crossover will be instituted in transitioning clinics to ensure patients in the intervention group have had the opportunity to receive the QPL and endorsement letter from the surgeon. Study staff will notify enrolled

surgeons prior to the upcoming crossover as the intervention is dependent on surgeon endorsement. We expect negligible contamination between study arms as the intervention requires surgeon endorsement of the QPL. Only patients whose surgeons have crossed over into the intervention arm will receive the QPL and surgeon endorsement letter in the mail prior to consultation. Although patients in the control arm may access question lists from outside sources, our prior observational studies confirm surgeons do not routinely endorse the use of question prompts.

Whereas surgeons are not blinded to the intervention, every effort will be made to maintain blinding for patients and family members. Participants will be told the goal of the study is to evaluate communication between surgeons and patients, but they will not be informed about the distribution of the QPL. Transcriptionists and qualitative interviewers will be blinded to the intervention status of each encounter. Study staff are tasked with assuring the QPL has been sent and providing regular reminders to the surgeon to endorse the QPL with all new patients. Study staff will not know if the patient has received the QPL at the time of enrolment but will not be blinded during data collection. In an attempt to insulate study staff from group assignment during data collection, they will strictly adhere to a script and enquire about receipt of the QPL (with all patients regardless of group assignment) 1

Table 3 Mediating variables and covariates

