In qualitative interviews with a subset of participants who suffered a serious postoperative complication, we will use questions designed to explore the content of patient and family experience with perioperative conflict. The interview guide is structured around open-ended questions about perioperative events, including 'Tell me the story of your experience with surgery'.⁵⁸ The interviewer will follow up the respondents' narrative description with probing on the following domains: patient and family values and goals, decision making, interpersonal relationships (between surgeons and patients/family members, between treating physicians and between family members) and intrapersonal conflict (relating to post-treatment regret and self-blame). We will use feedback during concurrent coding and analysis to prompt additional questioning on emerging themes and trends.

Planned analyses

Quantitative analyses

Our primary analysis will compare the effectiveness of the QPL intervention relative to usual care in regard to patient engagement and patient psychological well-being. We will use an intention-to-treat analysis with all available data from participants based on group assignment. The intervention effect will be tested in the framework of generalised linear mixed-effects models^{59 60} with a treatment dummy variable, surgeon random effect and site-by-time dummy variables to control for site-specific secular trends. We will use linear mixed-effect models for continuous responses such as self-efficacy (PEPPI-5) and well-being (MYCaW), logistic random-effects models for binary responses such as post-treatment regret, and log-linear random-effect models for count-dependent variables such as the number and type of questions asked during the preoperative visit. For linear models, we will adjust for prespecified covariates to increase the statistical precision of our treatment effect estimation.

Our secondary analyses will examine other patient endpoints such as psychological well-being (PROMIS measures) and nature of treatment received. These analyses will also test for intervention effects in family member outcomes such as PEPPI-5, HCCQ, MYCaW, post-treatment regret and psychological well-being. We will use the generalised linear mixed modelling framework used in primary analyses for these outcomes. All models will be estimated and tested using PROC MIXED or PROC NLMIX in SAS V.9.3.

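### No primary model for the question types or regret adjusts for a patient-level covariate, although suitable covariates are collected and patients are recruited after their surgeon's allocation is fixed

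*Combined protocol and SAP*

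**What the plan says.** **SAP, General Analysis Plan.** The intervention effect is tested in generalized linear mixed models "with a treatment dummy variable, surgeon random effect and site-by-time dummy variables to control site-specific secular trends".

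**SAP, Updated analysis plan and modified power analysis.** PEPPI-5 and MYCaW stop being primary outcomes. Four question types (one binary, three ordinal) and regret (binary) remain. For the model, "This additional analysis of our primary endpoints is otherwise unchanged from our per-protocol plan". For regret: "We will use a logistic random effects model with a treatment dummy variable, surgeon random effect and site-by-time dummy variables".

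**SAP, Additional considerations: Aim-1 question asking.** After the intention-to-treat and restricted analyses comes one sentence: "Additional analysis will adjust for age and comorbidity". The corresponding Aim-2 regret section plans a three-level version of the outcome but no adjusted model.

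**Published protocol (appended), Quantitative analyses.** "For linear models, we will adjust for prespecified covariates to increase the statistical precision of our treatment effect estimation". The same paragraph assigns "logistic random-effects models for binary responses such as post-treatment regret" and log-linear models to question counts.

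**Published protocol, Table 3.** The listed covariates include Charlson score and indication (chart review, clinic visit) and age (patient, first questionnaire).

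**Published protocol, Recruitment, Randomisation and blinding, and Intervention.** The schedule of crossover waves is set at study start. Staff find eligible patients from clinic schedules, the QPL is mailed before the appointment if the surgeon has crossed over, and consent is taken on the clinic day. "Study staff are tasked with assuring the QPL has been sent", and they also remind surgeons to endorse it. The same paragraph says that staff will not know at enrolment whether a given patient received it.

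**The concern.** Randomising 40 surgeons protects the comparison of surgeons. It does not by itself make the patients who enrol before and after a surgeon's crossover comparable, because those patients are found and consented once the arm is settled. Intervention patients also decide on participation after the QPL has been mailed to them. If the patients enrolled after crossover differ in age or comorbidity from those enrolled before, the treatment term absorbs part of that difference.

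The trial plans to collect variables that could protect against this. The sponsor also expects indication and comorbidity to matter, since both are named for heterogeneity analyses. The plan nevertheless ranks the adjusted analysis below the unadjusted one for question asking and omits it for regret, the only remaining Aim 2 primary outcome. Two things are at stake: some precision, and protection against a within-surgeon shift in case mix.

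**Working it through.** **1. Which models carry patient covariates**

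| Endpoint | Primary model terms in the SAP | Adjusted analysis in the SAP | Adjustment promised in the published protocol |
|---|---|---|---|
| Options, Expectations, Risks (ordinal) | treatment, surgeon, site-by-time | additional; age and comorbidity | no (counts, log-linear) |
| Advance Directives (binary) | same | additional; age and comorbidity | no (counts, log-linear) |
| Regret (binary) | same | none stated | no (logistic) |

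**2. Reproducing the published power**

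Inputs from the published protocol: the Table 1 crossover schedule; 40 surgeons, 6 waves and 2 patients per surgeon per wave (480 in all); two-sided alpha 0.025; ICC from 0.05 to 0.30; fixed effects for site, wave and site-by-wave. The stated power is 82% at d = 0.425 and 93% at d = 0.5.

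Method: generalised least squares variance of the treatment effect, with total variance 1 and a surgeon random intercept. Power = Φ(d/SE − 2.241).

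- ICC 0.05: SE = 0.134. With d/SE = 0.425/0.134, power is 82.4%; at d = 0.5, it is 93.2%. Both match.
- ICC 0.30: SE = 0.1305. This gives 84.5% and 94.4%.
- Across the ICC range, power runs from 80.5% to 84.5% at d = 0.425 and from 92.0% to 94.4% at d = 0.5.

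The missing covariates therefore do not make the published figures wrong.

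**3. Effect of adjustment on precision**

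Assumption: covariates explain a share R² of the within-surgeon variance, so 0.70 becomes 0.70 × (1 − R²) at ICC 0.30. The documents give no R².

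| R² | SE ratio | SE | Power, d = 0.425 | Power, d = 0.5 |
|---|---|---|---|---|
| 0 | 1.000 | 0.1305 | 84.5% | 94.4% |
| 0.05 | 0.977 | 0.1275 | 86.3% | 95.4% |
| 0.10 | 0.953 | 0.1244 | 88.0% | 96.2% |

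Check of one cell: d/SE = 0.425/0.1244 = 3.416; subtracting 2.241 leaves 1.175, and Φ(1.175) = 88.0%.

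For regret (443 patients, alpha 0.05, ICC 0.30, full completion) the same method gives 95.9%, rising to 96.6% and 97.2%. There is little precision to gain there.

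**4. What a within-surgeon shift could do**

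This is an illustration only, since the documents give no imbalance. Let the imbalance be the difference in a covariate between arms that remains after the surgeon and site-by-time terms, in SD units. Spurious log OR = ln(OR per SD) × imbalance. For the type I error, divide by π/√3 = 1.814 and by the SE for 443 patients (0.139 at ICC 0.05, 0.135 at ICC 0.30), with nominal alpha 0.0125.

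| OR per SD | Imbalance | Spurious OR | Share of ln 1.3 | Type I error |
|---|---|---|---|---|
| 1.2 | 0.1 SD | 1.02 | 7% | 0.013 |
| 1.5 | 0.2 SD | 1.08 | 31% | 0.017 |
| 2.0 | 0.3 SD | 1.23 | 79% | 0.048 to 0.050 |

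Middle row: ln 1.5 × 0.2 = 0.081; exp(0.081) = 1.08; 0.081/0.262 = 31%. The result runs from negligible to serious, depending wholly on the assumed shift.

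**The case against.** **The design already limits the problem.** Patients must be identified at least 5 days ahead in both arms. There is a two-week hiatus at crossover. Enrolment per surgeon and wave is capped (two in the published protocol, up to three in the SAP). Participants are not told about the QPL, wave changes ignore treatment group, and the DMC reviews demographic balance. The surgeon effect and site-by-time terms absorb stable differences between surgeons and common trends. All of this stands, and the documents offer no evidence of differential recruitment. But none of these measures adjusts the treatment effect if the patients of one surgeon change at crossover.

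**The plan already has an adjusted analysis.** That is true for question asking. Regret has none, and the heterogeneity analyses of indication and comorbidity are not adjustment.

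**Stronger readings that the documents do not support:**

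- A reader might infer that the SAP broke a published promise to adjust. The promise covered linear models only. For the original primaries that means PEPPI-5 and MYCaW, neither of which is primary in the modified plan.
- A reader might infer that recruiters knew who had received the QPL. The published protocol says they did not know this at enrolment. They could know the surgeon's arm, which is a weaker exposure.
- A reader might take a crude two-arm imbalance in oncologic patients as the bias of the planned model. Indication probably follows surgeon subspecialty to some extent, so part of such a difference is chance imbalance between surgeons, partly absorbed by the surgeon effect and covered by the test's error rate. Only within-surgeon change counts here.
- A reader might apply the power gain to the SAP's 85% for an odds ratio of 1.3. That figure does not come out of this stepped-wedge method (about 6-8%). It is a separate matter and no base for a gain.

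**Conclusion.** The point holds as an improvement to the primary analysis. Every retained primary model lacks patient covariates, the adjusted analysis is secondary and limited to Aim 1, and suitable covariates are already collected in a design that recruits after allocation.

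The precision gain is modest: about 2 to 3.5 power points (84.5% to 86.3-88.0%) at d = 0.425, ICC 0.30 and alpha 0.025, if R² is 5-10%. It rests on an assumed R² and a linear model. In logistic and ordinal models adjustment also changes the odds ratio being estimated, so the figure is only indicative. The better reason to adjust is protection against a within-surgeon shift in case mix, whose size the documents do not allow anyone to state. Adjustment removes only the part carried by the measured covariates.

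**What to change.** Before unblinding, amend the SAP as follows:

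1. Make the primary mixed models for the four question types and regret include age, Charlson score and indication, alongside the existing terms. State the functional form of each.
2. Take indication from chart review, not from the recorded consultation, which follows delivery of the QPL. Use three levels: oncologic, vascular, and other or neither. The third is needed because the SAP allows that some enrolled patients turn out to have neither problem.
3. Give a rule for missing covariates so that no intention-to-treat patient drops out for lack of one. Age is listed as coming from the first questionnaire, which 97% of patients had completed when the SAP was written; at that rate about 0.03 × 443 = 13 patients would lack it. Taking age from the chart, or single imputation, would suffice.
4. Keep the unadjusted models as supportive and report both.
5. Do not adjust for family presence at the visit, because the SAP itself says that the QPL may change it.

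The cost is SAP wording and a few extra model terms. The primary odds ratio becomes conditional on the covariates, and the report should say so.
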